### **3. STUDY AIMS/STUDY OBJECTIVES**

The goal of this research is to test the accuracy of PET/MRI imaging with F-fluorofuranyl norprogesterone (FFNP) for measuring progesterone receptor (PR) expression in patients with invasive breast cancer. We hypothesize that FFNP SUVmax from PET/MRI will correlate well against the semi-quantitative PR immunohistochemistry score.

#### 3.1 Primary objective:

To compare FFNP uptake of biopsy-proven primary PR+ breast malignancies measured using PET/MRI with the reference standard of PR immunohistochemistry (IHC).

#### 3.2 Secondary objectives:

- To determine the test-retest reproducibility of quantitative assessment of tumor FFNP uptake.
- To determine the intra- and inter-observer variability of quantitative assessment of tumor FFNP.
- To evaluate the optimal cut-point of FFNP uptake for distinguishing between PR-negative and PR-positive invasive breast cancer.
- Estimate the association of tumor FFNP uptake (continuous SUVmax) with research-based Oncotype DX scores (0-100)

#### 3.3 Exploratory objectives:

- To evaluate heterogeneity of tumor FFNP uptake.
- To correlate tumor FFNP uptake with serum progesterone and estradiol levels.
- To correlate tumor FFNP uptake with disease recurrence.

Study duration: 36 months. Our estimated rate of accrual is 1 participant per month.

## 4. SELECTION OF PATIENTS

### Study Population:

Female patients of all races and ethnic backgrounds at least 18 years of age with a current diagnosis of invasive breast cancer who are undergoing breast MRI for staging and extent of disease ordered by their provider as part of routine clinical care.

#### 4.1 Eligibility Criteria

##### Inclusion Criteria:

- 4.1.1 Women 18 years of age or older
- 4.1.2 Diagnosis of biopsy-proven invasive breast cancer measuring at least 1.0 cm in diameter by any imaging modality
- 4.1.3 Biopsy-proven PR-positive or PR-negative invasive breast cancer
- 4.1.4 Undergoing diagnostic breast MRI ordered by the referring clinician for staging and extent of disease†

##### Exclusion Criteria:

- 4.1.5 Inability or unwillingness to provide informed consent to the study
- 4.1.6 Patients who have had neoadjuvant chemotherapy/endocrine therapy, surgical intervention, or radiation for the current biopsy-proven malignancy
- 4.1.7 Patients with breast expanders
- 4.1.8 Patients who are or might be pregnant or lactating
- 4.1.9 Patients with a contraindication to gadolinium based contrast agents, including allergy or impaired renal function (per UW Health Guidelines)
- 4.1.10 Patients with a history of allergic reaction attributable to compounds of similar chemical or biologic composition to FFNP
- 4.1.11 Patients in liver failure as judged by the patient's physician
- 4.1.12 Patients with standard contraindications to MRI, including claustrophobia and metallic implants incompatible with MRI
- 4.1.13 Patients requiring conscious sedation for imaging are not eligible; patients requiring mild, oral anxiolytics for the clinical MRI scan will be allowed to participate as long as the following criteria are met:
  - 4.1.13.1 The patient has their own prescription for the medication

---

† Patients with newly diagnosed invasive breast cancer from a screening breast MRI are eligible to participate in this research. For these subjects, the research breast PET/MRI should be performed prior to any treatment or surgery for the invasive breast cancer.

- 4.1.13.2 The informed consent process is conducted prior to the self-administration of the medication.
  - 4.1.13.3 The patient comes to the research visit with a driver.
- 4.1.14 Patients unable to lie prone for 30 minutes for imaging

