## NUMBER OF SUBJECTS

---

[figure not shown]
\* Patients with newly diagnosed invasive breast cancer from a screening breast MRI are eligible to participate in this research. For these subjects, the research breast PET/MRI should be performed prior to any treatment or surgery for the invasive breast cancer.

The primary objective is to compare FFNP  $SUV_{max}$  from PET/MRI with the PR immunohistochemistry semi-quantitative score obtained by using the Allred score (0-8) (1). The correlation of the two measures will be evaluated with Pearson's correlation coefficient. The null hypothesis is  $H_0: p_0=0.20$  and the alternative hypothesis is  $H_1: p_1=0.70$ .

A sample size of 21 patients achieves 80% power to detect this difference, using a one-sided hypothesis test with a Type I error of 5%, accounting for 1 dropout. Up to 5 subjects with PR-negative breast cancer will be enrolled.

To measure test-retest reproducibility, a subset of up to 5 PR+ participants will have test-retest FFNP scans.

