**Table 2: Study Calendar/Schedule**

Study Activity	Baseline a	Imaging Day b	Clinical Follow-Up c
Informed Consent h	X		
Demographics d	X		
Medical History d	X		X
Radiology Reports d	X		X
Pathology Reports (Breast biopsy and final surgical excision) d	X		X
Concomitant Medication Review		X	
Pre-Scan Pregnancy Test (if needed)		X	
Day of last menstrual period (if premenopausal)		X	
Height and Weight		X	
Vital Signs e		X	
Blood for Hormone Levels		X	
FFNP-PET/MRI i		X j	
Adverse Event Evaluation f		X	X
Research-based Oncotype DX Score g			X

- (a) Baseline is defined as the time period from initial subject contact until injection of FFNP.
- (b) Imaging Day is defined as the day of the research FFNP-PET/MRI session.
- (c) Any standard of care clinical visits, labs, or imaging exams obtained during this time period will be reviewed from the electronic medical record to correlate with scan results.
- (d) Clinical data, including age, primary breast cancer data (standard clinical histopathology including ER/PR/HER2/Ki-67, location, size, and date of biopsy/diagnosis), Oncotype Dx recurrence score (if obtained clinically), mammographic breast density, and menopausal status will be recorded. If premenopausal, menstrual cycle data will be recorded.
- (e) Vitals signs (blood pressure, heart and respiratory rate, and temperature) will be measured before FFNP injection, after FFNP injection, and after the PET/MRI scan.

- (f) Adverse events occurring within a 24-hour period post-FFNP infusion will be recorded by the study coordinator who will contact the subject within 1 to 3 days.
- (g) A research-based Oncotype DX assay will be performed using the resection specimen, if remaining tissue is available.
- (h) During the COVID-19 pandemic, consent procedures will be conducted by phone, when possible, to minimize face-to-face contact subjects have with the research team. An encrypted copy of the consent form will be mailed or emailed to subjects prior to the scheduled consent phone call.
- (i) Subjects who are unable to undergo a PET/MRI scan will be invited to undergo a PET/CT scan in addition to separate MRI scan.
- (j) For subjects participating in the test-retest cohort, the second scanning session will be done 24 hours apart or within a maximum 14-day time frame.

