### **5.5.3 FFNP Administration**

The patient will have an intravenous line placed, typically in the hand or arm opposite to the known primary breast cancer, FFNP will be given by a slow infusion (approximately 2 minutes), and the dose administered will be approximately 7 mCi. The injection site will be inspected by the technologist to assess for any possible infiltration. Vital signs (blood pressure, heart and respiratory rate, and temperature) will be taken after injection. The patient will wait approximately 60 minutes to allow for biodistribution and tumor uptake of the radiopharmaceutical prior to imaging. The patient should void immediately prior (5-10 minutes) to image acquisition. Vital signs (blood pressure, heart and respiratory rate, and temperature) will be taken after the PET/MRI acquisition is complete.

All adverse events occurring within a 24-hour period post-FFNP infusion will be recorded (a phone call to the participant is acceptable means of collecting this information). The adverse events to be specifically monitored during the infusion include localized discomfort at the IV injection site, pain, respiratory difficulties, flushing, dizziness, pruritus/rash, and any other symptoms that could be secondary to an anaphylactic reaction. The subject will be instructed to report any subjective symptoms or sensory changes noted.

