### 5.5.5 Research Imaging Acquisition

Image acquisition and reconstruction protocols specific to this research study will be available in a separate "Imaging Manual". The protocol is briefly described here.

The breast PET/MRI will be acquired using the GE Discovery 750W 3T MR scanner containing the PET insert and an 8-channel breast coil qualified for PET/MRI located in the basement level of WIMR Tower 1. Directed breast PET/MRI data will be acquired with the patient in the prone position. Imaging will be performed by research technologists under guidance of the principal and/or collaborating investigators. MRI-sequences utilized in a standard clinical breast MRI will be obtained, including T1-weighted imaging without fat suppression and T2-weighted fat suppressed and diffusion weighted imaging (DWI) prior to gadolinium contrast administration followed by T1-weighted fat suppressed DCE imaging. The MRI sequences will include standard clinical sequences and may include research MRI sequences under development and evaluation at the University of Wisconsin. The standard MR-based attenuation correction algorithm provided by GE will be used for this study. The MRI sequence(s) will be co-registered to the PET data for motion correction. Breast specific PET emission data will be acquired simultaneous with the MR images (Figure 1). The entire examination is expected to take 30 – 40 minutes.

**Figure 1:** Simultaneous acquisition of PET events during the acquisition of the MRI sequences. PET data will be segmented and motion corrected corresponding to the anatomic position as determined by the MRI sequence coinciding with the PET data acquisition.

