#### 6.5 Criteria for Removal from Study

Enrolled patients will be removed from the study in the following circumstances:

- The patient does not complete the PET/MRI examination per study protocol
- Pregnancy
- The subject withdraws consent
- Exclusion criteria are discovered after registration
- The patient has a contrast reaction to the gadolinium based contrast agent utilized for the clinical breast MRI

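### The prone-tolerance exclusion matches the shortest expected PET/MRI session and may fall up to 10 minutes short of the longest (minor)

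*Combined protocol and SAP*

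**What the plan says.** The last exclusion in the Protocol Summary and criterion 4.1.14 use the same words: "Patients unable to lie prone for 30 minutes for imaging".

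Section 5.5.5 describes the research scan. "Directed breast PET/MRI data will be acquired with the patient in the prone position", and "The entire examination is expected to take 30 – 40 minutes". T1-weighted, T2-weighted and diffusion-weighted imaging are listed "prior to gadolinium contrast administration followed by T1-weighted fat suppressed DCE imaging", so the contrast series comes last. PET is acquired at the same time as the MRI. The section allows research MRI sequences to be added and does not say whether the stated duration includes them.

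The tracer is given before tolerance is tested. Section 5.5.3 states: "The patient will wait approximately 60 minutes to allow for biodistribution and tumor uptake of the radiopharmaceutical prior to imaging". Section 16.1.2 puts the effective dose equivalent at about 5 mSv.

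One of the grounds for removal in 6.5 is: "The patient does not complete the PET/MRI examination per study protocol". The section does not define a partial examination. The sample size of 21, in the Summary (Number of Subjects) and in 12.1.1, is stated as "accounting for 1 dropout". No replacement rule is given.

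There is a fallback. Table 2, note (i) reads: "Subjects who are unable to undergo a PET/MRI scan will be invited to undergo a PET/CT scan in addition to separate MRI scan". The last paragraph of 5.5.3 gives body size and scanner faults as examples. It puts the separate MRI at roughly 30 to 40 minutes and performs the PET/CT prone, in 15 to 20 minutes.

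**The concern.** The criterion is there to make sure that an enrolled patient can finish the scan, yet its threshold sits at the bottom of the protocol's own range of durations. A woman who can lie prone for 30 to 35 minutes is eligible. She would be injected, wait an hour, and might be unable to finish a session that runs to 40 minutes. Section 6.5, read literally, then removes her.

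Two things are at stake. One is radiotracer exposure that yields no evaluable primary endpoint. The other is the number of evaluable patients: the plan allows one loss for all causes together, including withdrawn consent, tracer or scanner failure and exclusions found late (6.5 and 16.1.4).

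**Working it through.** **Step 1: the durations.** The screen is 30 minutes (4.1.14 and Summary). The session is 30 to 40 minutes (5.5.5).
- Shortfall at the lower end: 30 − 30 = 0 minutes.
- Shortfall at the upper end: 40 − 30 = 10 minutes, if the whole session is spent prone.

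The documents do not divide the session into set-up and prone scanning, so the gap lies between 0 and 10 minutes.

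**Step 2: what has been acquired when such a patient stops.** If the prone time is P ≤ 40 minutes, a woman who lasts 30 minutes has completed 30/P ≥ 30/40 = 75% of it. One who lasts 35 minutes has completed at least 35/40 = 87.5%. This is a share of time, not of PET counts, and the documents give no minimum acquisition for a valid SUV. Because PET runs alongside the MRI and the contrast series comes last, the DCE series is the part most likely to be lost.

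**Step 3: exposure.** 259 MBq × 0.02 mSv/MBq = 5.18 mSv, which 16.1.2 rounds to about 5 mSv.

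**Step 4: reproduce the planned sample size.** Inputs from 12.1.1 are a null correlation of 0.20, an alternative of 0.70, 80% power, and a two-sided 5% test. Fisher z gives

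n = [(z_α + z_β) / (atanh 0.70 − atanh 0.20)]² + 3 = [(1.960 + 0.842) / (0.8673 − 0.2027)]² + 3 = 20.8.

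That rounds up to 21, with 78.2% power at n = 20. Simulating the correlation test under bivariate normality (400,000 replicates, critical value taken at 0.20) gives 80.2% at n = 20. So 20 evaluable plus 1 dropout reproduces the stated 21. The one-sided test in the Summary does not reproduce it: Fisher z gives [(1.645 + 0.842)/0.6646]² + 3 = 17.0, and the simulation reaches 80% at n = 16.

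**Step 5: power as losses accumulate, without replacement.**

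| Evaluable (lost of 21) | Two-sided, simulated | Two-sided, Fisher z | One-sided, simulated | One-sided, Fisher z |
|---|---|---|---|---|
| 20 (1) | 80.2% | 78.2% | 88.0% | 86.3% |
| 19 (2) | 77.8% | 75.8% | 86.3% | 84.5% |
| 18 (3) | 75.5% | 73.0% | 84.5% | 82.4% |
| 17 (4) | 72.2% | 70.1% | 82.3% | 80.0% |
| 16 (5) | 69.6% | 66.9% | 80.1% | 77.4% |

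The first loss beyond the allowance costs 80.2 − 77.8 = 2.4 points of two-sided power. Later ones cost about 2 to 3 points each.

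**Step 6: how often the allowance would be exceeded.** One loss in 21 is 1/21 = 4.8%. The documents give no non-completion rate, so p below is an assumed loss rate from all causes. The chance of two or more losses is 1 − (1 − p)²¹ − 21p(1 − p)²⁰.
- p = 2%: 6.5%. Enrollment needed for 20 evaluable: 20/0.98, rounded up to 21.
- p = 5%: 28.3%. Enrollment needed: 20/0.95, rounded up to 22.
- p = 10%: 63.5%. Enrollment needed: 20/0.90, rounded up to 23.

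Inability to stay prone contributes only part of any such rate.

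**The case against.** The strongest reply is that the two figures measure different things. The criterion concerns time lying prone, whereas 5.5.5 gives the length of the session, so the real gap could be nil. That stands, and it is why the shortfall is given as 0 to 10 minutes.

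Second, a reader might infer that a patient who stops early yields no usable data. The documents do not support that. The primary measure is SUVmax (12.1.1). Section 5.5.6 guides the ROI by lesion extent on anatomic imaging and locates the lesion from the prior clinical MRI or earlier imaging. Nothing makes SUVmax depend on a complete DCE series. Data would be lost mainly through the undefined completion rule in 6.5.

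Third, a reader might infer that gadolinium would be given for nothing. A patient who stops before the contrast series receives none, and one who stops during it has already finished the pre-contrast sequences.

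Fourth, many participants will already have tolerated a comparable clinical breast MRI, because 4.1.4 requires one to be ordered. This lowers the likely number of failures but does not remove them: under 5.1 the clinical scan need not come first, and under section 7 the MRI component may itself serve as the clinical examination.

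Fifth, there is the PET/CT fallback. It helps only in part. It is also prone, its separate MRI is just as long, and its examples do not include inability to stay prone. Neither 6.5 nor Table 2 says whether a fallback scan counts as completing the PET/MRI.

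**Conclusion.** The mismatch is real and minor. The screen equals the lower end of the protocol's stated duration and may be up to 10 minutes short of the upper end. A woman who passes it could receive about 5 mSv of tracer, fail to finish and be removed, even though much of her PET and pre-contrast MRI may already be in hand.

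A reader might infer that one or two patients in 21 would be lost this way, or that the trial would be seriously underpowered. Neither follows. The first needs a rate of 5 to 10% (21 × 0.05 = 1.05; 21 × 0.10 = 2.1), which the documents do not give. On the second, each loss beyond the first costs about 2 to 3 points under the two-sided plan, and under the one-sided wording power stays at or above 80% down to about 16 or 17 evaluable patients. That conflict over sidedness is a separate matter; only the two-sided version reproduces 21.

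The power figures assume bivariate normality, no replacement, and that the 21 are the patients in the primary analysis.

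**What to change.** - **4.1.14 and the Summary exclusion:** reconcile both with 5.5.5 by tying the prone-tolerance criterion to the maximum prone scan time that the protocol states. State in 5.5.5 how much of the session is spent prone and whether research sequences are included.
- **Timing:** confirm tolerance with the patient before the tracer is ordered.
- **6.5:** let a patient whose PET data and lesion-localizing MRI are adequate for SUVmax stay in the primary analysis even if the DCE series is incomplete. Adequacy should be judged without sight of the Allred score. State also whether fallback scans count as completed and whether removed patients are replaced.

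The cost is a short amendment, and a few borderline patients would not be enrolled, some of whom might have given usable PET data. Accrual can probably bear this. Taking the 21 plus up to 5 PR-negative patients as at most 26, one per month uses 26 of the 36 months, although the one-year minimum follow-up for recurrence draws on the same period.

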## 5. RESEARCH DESIGN AND METHODS

### 5.1 Study Design

This prospective, one-arm, single-institutional research study will enroll patients with invasive breast cancer scheduled for diagnostic breast MRI for preoperative staging/extent of disease evaluation. Eligible patients will be consented for participation in the research study which will be performed on a separate day from the clinical breast MRI, if already performed, but prior to surgery. Ideally, the research breast PET/MRI study should be performed prior to any interventions (i.e. biopsies) prompted by the clinical breast MRI if performed prior to the research study, but this is not required. The results of the FFNP-PET/MRI will not be used to guide patient management. However, the clinical breast MRI component of the examination will be interpreted and reported with management recommendation as per routine clinical care. Surgical management, radiation therapy, and adjuvant therapy will follow standard of care. A research-based Oncotype DX score will be obtained from the surgical specimen for research purposes only. The proposed work-flow is described in the schema above.

### 5.2 Reference Standard

The primary objective is to measure FFNP uptake of biopsy-proven primary PR+ invasive breast cancer using PET/MRI. The reference standard will be PR expression measured with immunohistochemistry performed as per the current standard of care.

At UW Health, PR status is routinely reported as positive or negative and includes a visual estimation of the percentage of cells staining positive as well as intensity of staining. This information will be obtained from the pathology report in the subject's electronic medical record and will be used to calculate a semi-quantitative Allred score (1). If the information needed to calculate the Allred score is not included in the clinical pathology report, a pathologist on the research study team will review the existing PR IHC slides. Comparison of FFNP uptake with PR IHC expression will be performed as previously described for F-fluoroestradiol and ER IHC (15).

The Allred score is the sum of the proportion score and the intensity score (**Table 1**) (1). PR-negative cancers can have either an Allred score of 0 or 2 (1+1). PR-positive cancers can have an Allred score of 3, 4, 5, 6, 7, or 8. An Allred score of 1 does not exist.

**Table 1: Allred Scoring System**

Percentage of Positive-Staining Tumor Cells	Proportion Score (PS)	Average Intensity of Positive Tumor Cells	Intensity Score (IS)
None	0	None	0
<1%	1	Weak	1
1-10%	2	Intermediate	2
10-33%	3	Strong	3
33-66%	4		
66-100%	5		

### 5.3 Study Calendar/Schedule

The study calendar/schedule is detailed in **Table 2**.

**Table 2: Study Calendar/Schedule**

Study Activity	Baseline a	Imaging Day b	Clinical Follow-Up c
Informed Consent h	X		
Demographics d	X		
Medical History d	X		X
Radiology Reports d	X		X
Pathology Reports (Breast biopsy and final surgical excision) d	X		X
Concomitant Medication Review		X	
Pre-Scan Pregnancy Test (if needed)		X	
Day of last menstrual period (if premenopausal)		X	
Height and Weight		X	
Vital Signs e		X	
Blood for Hormone Levels		X	
FFNP-PET/MRI i		X j	
Adverse Event Evaluation f		X	X
Research-based Oncotype DX Score g			X

- (a) Baseline is defined as the time period from initial subject contact until injection of FFNP.
- (b) Imaging Day is defined as the day of the research FFNP-PET/MRI session.
- (c) Any standard of care clinical visits, labs, or imaging exams obtained during this time period will be reviewed from the electronic medical record to correlate with scan results.
- (d) Clinical data, including age, primary breast cancer data (standard clinical histopathology including ER/PR/HER2/Ki-67, location, size, and date of biopsy/diagnosis), Oncotype Dx recurrence score (if obtained clinically), mammographic breast density, and menopausal status will be recorded. If premenopausal, menstrual cycle data will be recorded.
- (e) Vitals signs (blood pressure, heart and respiratory rate, and temperature) will be measured before FFNP injection, after FFNP injection, and after the PET/MRI scan.

- (f) Adverse events occurring within a 24-hour period post-FFNP infusion will be recorded by the study coordinator who will contact the subject within 1 to 3 days.
- (g) A research-based Oncotype DX assay will be performed using the resection specimen, if remaining tissue is available.
- (h) During the COVID-19 pandemic, consent procedures will be conducted by phone, when possible, to minimize face-to-face contact subjects have with the research team. An encrypted copy of the consent form will be mailed or emailed to subjects prior to the scheduled consent phone call.
- (i) Subjects who are unable to undergo a PET/MRI scan will be invited to undergo a PET/CT scan in addition to separate MRI scan.
- (j) For subjects participating in the test-retest cohort, the second scanning session will be done 24 hours apart or within a maximum 14-day time frame.

